#### **4.2 Training Phase: Training School Partners to Lead OST-S Groups**

The **initial training** of school partners is described above in section 3.1.2.

Following the initial training, school partners will receive weekly or twice weekly **consultation and coaching** to support high fidelity implementation of OST-S. Consultation and coaching may be conducted in-person, over the phone, or through a web-based HIPAA compliant video-conference software approved by CHOP (a combination of these modalities may also be used). The frequency/duration of meetings as part of Consultation and Coaching will also take into consideration if a school partner has already been trained in and run the OST-S intervention in a prior year(s) of participation. If this is the case, the frequency/duration of these meetings may be adjusted from what is detailed below.

Consultation sessions (approximately 20 minutes per week) will be designed to prepare the school partner for the upcoming group session (e.g., review of key components of intervention during the session, plan for encouraging active involvement of student participants). Coaching sessions (approximately 20 minutes per week) will include a detailed review of the previous session with performance feedback for the school partner. Additional consultation and coaching may be provided during the weeks when parent and teacher meetings take place.

As indicated above, all OST-S sessions (student group and teacher and parent contacts) will be video and/or audio recorded, and the study team trainer will view the videos and listen to the audio to identify examples of effective implementation and areas for improvement. During the coaching session, the study team trainer will review brief segments of the video and/or audio (i.e., examples of effective and ineffective implementation) with the school partner and provide specific performance feedback regarding the extent to which OST-S program components were delivered accurately and competently (i.e., to encourage high rates of content and process fidelity). In addition, the study team trainer and school partner will discuss and practice strategies to address implementation difficulties and address concerns about individual students that may arise. Consultation and coaching sessions between the study team trainer and school partner will be videotaped (and may be audio recorded separately as a back-up method) used in supervision of the study team trainer.

School partners assigned to the TAU condition will not receive any training until the second year of participation after 12-month follow-up data have been collected.

---

### 4.3 Intervention Implementation

**TAU Control Condition:** As noted previously, students enrolled in the TAU condition will only receive support from their teachers and school staff that they would typically receive if not enrolled in this study.

**Table 2. Participants in TAU Control Condition:**

| YEAR | STUDENTS/PARENTS  | SCHOOL PARTNERS   | TEACHERS  |
|------|---|---|---|
| 1    | Research Participants:
Providing data at 4 time points                   | Collaborator: Support recruitment

Research Participant: Complete Demographic Form;   | Collaborator: Support recruitment

Research Participant: Complete Demographic Form;   |
| 2    | Recipient of Free, Clinical Intervention; no data collected; no recordings. | Collaborator: Implement Clinical Intervention as a Professional Development Experience; no data collected

Research Participant: Complete Demographic Form if new to study; | Collaborator: Participate in Clinical Intervention as a Professional Development Experience; no data collected

Research Participant: Complete Demographic Form |

\*It is anticipated that teachers in Years 1 and 2 will be different people.

**OST-S Condition:** OST-S is a small group skills training intervention, implemented by the trained school partner, with parents and teachers supporting students' use of new skills. Each small group session includes: (a) homework review to assess completion of between-session skills implementation; (b) skill-building activities, which include the use of modeling, shaping, guided practice, and reinforcement for organized behavior; and (c) activities to promote generalization of skills.

Sessions address four organizational challenges to students: (a) tracking assignments, (b) managing materials, (c) managing time, and (d) planning for long-term assignments.

**Procedures to promote parent and teacher involvement and student skills generalization.** Once parental consent and student assent are obtained, the school partner will meet with the parent (ideally in-person but phone or web-based video software typically used by schools to engage with families virtually may also need to be utilized). The purpose of the initial meeting between the school partner and parents is to explain OST-S in more detail, increase parent investment in participation, and ensure that parents understand their role in the intervention. The school partner and parent will collaboratively identify goals for the student related to OTMP skills (e.g., bringing home needed papers, writing down homework), and the school partner will explain how OST-S can be helpful in addressing those goals. Furthermore, the school partner will schedule 1 additional meeting, approximately 30-minutes in duration. The meetings will ideally be held in-person, but could be done by phone or web-based video software (typically used by schools to engage with families virtually) if it is not possible to meet in person. We could also allow for an email exchange if necessary. During these meetings (or contacts with the parent), the school

partner will review OST-S strategies and collaboratively design home-based methods for parents to prompt, monitor, and reinforce the skills students have learned. At the initial parent meeting, parents will be given a manual that provides specific guidelines to them about how to promote the implementation of their student's OTMP skills. These parent meetings will be audio and/or video recorded. If there is only an email exchange, the email will be printed and coded as study data in place of the video/audio recording.

Also, after parent consent is obtained, the school partner will arrange a meeting with the student's teacher (ideally in-person but phone or web-based video software typically used by schools to engage with families virtually may also be utilized). For feasibility purposes, this meeting might occur individually with teachers or in a group format for all of the teachers of students involved in the group. The purpose of the meeting is to review the goals of OST-S, encourage teacher buy-in, introduce the use of positive behavior supports to encourage skill change, and collaboratively plan for use of OST-S strategies in the classroom (e.g., Daily Assignment Record). After the initial meeting, the school partner will schedule 1 additional 15-minute consultation session with the teacher to review student's progress toward goals and discuss implementation of OST-S strategies in the classroom (ideally in-person but phone or web-based video software typically used by schools to engage with each other virtually may also be utilized). School partners will give teachers handouts after each student session to inform teachers about session content and tips for integrating OST-S strategies into the classroom. These teacher meetings will also be video and/or audio recorded and evaluated by the study team as implementation fidelity data.

The goals of the parent and teacher-mediated components are to: (a) address generalization challenges by promoting student use of OTMP skills at school and home, and (b) increase students' academic self-efficacy.

**Table 3. Participants in Intervention (OST-S) Intervention Condition:**

| YEAR | STUDENTS/PARENT   | SCHOOL PARTNERS   | TEACHERS   |
|------|---|---|--|
| 1    | Research Participants:
Participate in recorded OST-S Intervention & provide data at 4 time points | Research Participant:
Implement recorded OST-S Intervention with Students, Parents and Teachers; Complete Demographic Form and additional measures; Support Recruitment | Research Participants:
Participate in recorded OST-S Intervention & provide data at 4 time points; Support Recruitment |

\*\*Students, School Partners and Teachers in the **Intervention Condition** are all Research Participants as their participation in the intervention is recorded and evaluated for study outcomes.

## 5 STUDY EVALUATIONS AND MEASUREMENTS

The table on Page vi (*Table 1. Timeline of Study Evaluation and Measurement Completion*) summarizes the sections to follow with detailed descriptions of the study evaluations and measurements. Phone, text, and email are means of communication that may be utilized to get in touch with families and school staff members to schedule meetings for data collection. The study team may communicate with the subject via text after the subject provides their permission for this method of communication.

### 5.1 Screening Measures (Students)

Teachers will be asked to complete a short form to indicate the extent to which the student's difficulty with organizational skills negatively impacts the student's academic performance. The teacher must rate the student's OTMP skills deficits as having a negative impact on academic performance (using items 39-42 of the COSS-T) by rating one of the four items  $\geq 3$  on 4-point scale (COSS-T; [name] & [name], 2009). The study team has obtained a waiver of consent to conduct this screening procedure.

---

## 5.2 Measures of Proximal Outcomes and Mediators – OTMP Skills and Student Academic Self-efficacy

Measures will be completed at baseline, post-treatment, and at 5-month and 12-month follow-up.

**Children's Organizational Skills Scale, Parent (COSS-P) and Teacher (COSS-T) Versions.** The COSS-P and COSS-T ([name] & [name], 2009) will be used to assess OTMP functioning at home and school. COSS total scores have good discriminant validity and are sensitive to treatment effects ([name] et al., 2013; Pfiffner et al., 2013). Each COSS version uses a 4-point rating scale (1=*Hardly ever or never* to 4=*Just about all of the time*). Although the COSS yields three subscale scores, only the total score will be used to reduce the number of measures in the analyses.

**Patterns of Adaptive Learning Scales – Academic Efficacy Subscale (PALS).** The 5-item Academic Efficacy subscale of the PALS (Midgley et al., 1998) will be used to evaluate students' perceptions of their competence in completing their classwork. Items are rated on a 5-item scale from 1 = not at all true to 5 = very true.

## 5.3 Measures of Distal Outcomes – Academic Outcomes

Measures will be completed at pre- and post-treatment, and at 5-month and 12-month follow-up.

**Academic Progress Report** (APR; [name] et al., 2013). The APR is a teacher-report measure that assesses proficiency in seven academic subjects relative to standard expectations (1=*Well below standard* expected at this time of year; 3=*At standard*; 5=*Well above standard*). The sum of ratings across seven academic subjects is the unit of analysis. Reliability is acceptable ( $\alpha = .84$ ), and this measure is sensitive to OST treatment effects ([name] et al., 2013).

**Academic Competence Evaluation Scales** (ACES; DiPerna & Elliott, 2000). The ACES is a teacher-report scale that assesses the academic competence of students in kindergarten through grade 12. The Reading/Language Arts and Math subscales of this measure will be used. Alpha coefficients and test-retest correlations for these subscales have been shown to be above .90. The average of these subscale scores will be used in the analyses.

**Academic Grades.** We will obtain student report card grades for students in OST-S/TAU. We will calculate students' grade point average based on report card grades.

**Homework Survey:** Teachers will be asked to complete one question related to the percentage of homework assigned (in the school year to date) that they student has turned-in.

**Homework Performance Questionnaire – Teacher Version** (HPQ-T). The HPQ-T assesses students' homework behavior during the past 4 weeks. Each item is rated on a five-point scale. The 9-item Student Self-Regulation factor will be used in the analyses. This factor has been demonstrated to have strong psychometric properties ([name] et al., 2014).

**Homework Problem Checklist (HPC).** The HPC is a 20-item parent-report measure that assesses student homework performance. The psychometric properties of this instrument have been shown to be acceptable ([name] et al., 2006), and the HPC was sensitive to

treatment effects in the OST-C study ([name] et al., 2013). The total HPC score will be used in the analyses.

#### **5.4 Implementation Outcome Measures**

**Measures of Intervention Fidelity.** To ensure treatment components are delivered as intended, numerous treatment fidelity procedures will be implemented during each group. The procedures are based on those used in the OST-C study. Process fidelity procedures will be based on strategies used by Dumas and colleagues (2001) to train school staff. To assist with monitoring school partner process and content fidelity, checklists for each OST-S group session and parent and teacher meeting will be used. Checklists will be used in two ways. First, school partners will be encouraged to use the content and process fidelity checklists as a guide during sessions. Second, all student small group sessions will be video and audio recorded, and parent and teacher consultation meetings will be video and/or audio recorded. The study team trainer will observe each video (student group sessions) and listen to each video/audio (parent and teacher consultation meetings) and code content and process fidelity for use in consultation and coaching meetings. A separate member of the Intervention Core team who is not directly involved with a school, will watch 50% of the videos for each group that are selected at random and code content and process fidelity for use as research data. A member of the Intervention team supervisory staff will function as the 'Gold Standard' coder and will code a randomly selected 25% of the videos, which are selected for content and process coding for use in calculating the reliability of the coding. When challenges are encountered in administering the intervention, portions of these videos may be viewed by the Intervention Core team ([name], [name], [name]) during weekly meetings. The Intervention Core will determine how best to address the situation in a manner that is consistent with the original intervention. [name] will watch videos of consultation and coaching sessions as needed to provide supervisory feedback on the study team trainer's implementation of the consultation and coaching procedure.

Fidelity content items will specify what to do during sessions and will be rated on a scale from 0 to 1 (0 = not implemented; 1 = implemented). These ratings yield a fidelity index, and represent the extent to which OST-S content is covered in each session. Process items for OST-S sessions (e.g., encouraging all persons to participate), will be rated on a scale from 0 to 4 (0 = rarely; 4 = all or almost all of the time; Dumas et al., 2001).

**Measures of Stakeholder Engagement.** Several measures of school partner, parent, student and teacher engagement in the program and adherence with procedures outside of sessions will be used. Research assistants will make note of student attendance and arrival time at each OST-S session. Also, using a measure used in the OST-C study ([name] et al., 2013) and based on their observation of the student session videotapes, study team members who are not directly involved with a group will watch the videos of a randomly selected 50% of student small group sessions per intervention group and listen to a randomly selected 50% of audiotapes of each parent and teacher consultation session and complete ratings for each group participant regarding the extent to which the student: (a) was engaged in in-session activities, (b) appeared to understand the new skill, and (c) was able to implement the new skill effectively. A second study team member will independently complete the same ratings for 25% of student group session and parent and teacher consultations selected for coding. Agreement between the study team coders will be calculated as a measure of the reliability of these ratings. At the conclusion of each session, OST-S homework assignments will be given. For example, students will be asked to write down their assignments daily in their new Daily Assignment Record (DAR). At the beginning

---

of the following session, RAs will collect all OST-S homework assignments. These assignments will be scored for completion and accuracy using the procedure developed by Drs. [name] and [name] (Clarke et al., 2013). The scoring system for student OST-S homework assignments has been adapted so that it provides a more useful index of student success in acquiring OTMP skills.

In addition, school partners will record parent attendance at parent consultation sessions and will indicate the extent to which the parent: (a) was engaged in discussions during the consultation, and (b) appeared to understand consultation content. A similar process will be used for teacher consultations. Furthermore, parents and teachers will generate permanent products (e.g., daily assignment record, home behavior chart). Students will be asked to bring those permanent products to the student group sessions and those permanent products will be collected and scored using the procedures developed by Drs. [name] and [name] (Clarke et al., 2013) to assess parent and teacher engagement in the generalization components of the program. If students forget to bring these permanent products to the student session, school partners will ask for them and make copies of them during parent and/or teacher consultations.

**Measures of Behavioral Change (Intervention Condition Only).** Organization and Planner Checklists (Evans et al., 2009; Sadler et al., 2011) will be used to assess how well students organize their academic materials and record their assignments in their planner. These checklists have been developed for middle and high school students with ADHD, and we have adapted them for use with elementary students. The criteria on the checklists are behaviorally defined. Scores for “Organization” and “Planner” are calculated by determining the percentage of criteria met (Sadler et al., 2011). Study staff will be trained to complete these checklists during the intervention group sessions. (*Please note: this measure will ONLY be collected when feasible within a particular school and based on research staff availability.*)

#### 5.4 Measures of School and Participant Characteristics

**School Characteristics** (as noted in Table 1.) will be collected by the study team about participating schools. This information will largely be obtained from publicly available data sources including (<https://nces.ed.gov/ccd/schoolsearch/>). **Teacher and parent ratings on the Behavior Assessment System for Children – third edition** (BASC-3, Reynolds & Kamphaus, 2015) will be used to assess child behavioral functioning. The BASC-3 has impressive psychometric properties. This measure will be given at baseline to characterize the sample and derive an index of ADHD, aggression, and internalizing problems for examination of potential moderation effects. If this measure is unable to be collected at baseline, an attempt will be made to collect it at a subsequent timepoint.

**Parent ratings on the Autism Spectrum Rating Scales (ASRS)-Short Form** (Goldstein, S. & Naglieri, J., 2012) – The ASRS Short Form is a 15-item scale designed to differentiate children with an Autism Spectrum Disorder from those in the general population, and those with other clinical disorders. High scores suggest that many behaviors associated with the Autism Spectrum Disorders have been observed. Parents are asked to evaluate how often they observed specific behaviors in the child in areas such as socialization, communication, unusual behaviors, behavioral rigidity, sensory sensitivity, and self-regulation. T-scores of 59 or less are within the normal range and usually suggest the absence of an autism spectrum condition. T-scores between 60 and 75 are generally considered above average or “at-risk” and indicate the presence of mild impairments in this area and the possible

presence of a mild autism spectrum disorder. T-scores of 76 or higher indicate severe impairments in this area and suggest that the child should be evaluated further for the presence of an autism spectrum disorder.

Parents/legal guardians/caregivers will be asked to complete this measure at post-treatment to reduce the burden on parents at the time of baseline data collection. If the measure is unable to be collected at post-treatment (aka approximately 8-weeks after baseline), it will be collected at either the 5-month follow-up or 12-month follow-up time-point. This measure will only be administered to the parent once about the student during the duration of study participation.

**Survey of Current Organizational Supports for Students** – This measure was developed by the investigative team. This measure will be administered to teachers (per student) to assess the current level of organizational supports being provided to students in their school environment (other than the OST-S intervention). This measure will be administered to teachers at post-treatment ONLY. If this measure is unable to be collected at post-treatment, an attempt will be made to collect it at a subsequent timepoint.

**Student Demographic Information** – To characterize the sample, demographic information will be obtained from school records, teacher report, and parent/legal guardian/caregiver report. Specifically, we will collect information about special education status, amount of special education services being offered, IEP goals, services being provided to address organizational problems, school counseling services, medication status, and current organizational, supervision, and homework systems in place at school and home. An area of deprivation index (ADI) which reflects a geographic areas level of socioeconomic deprivation will also be determined for participants to aid characterizing the samples socioeconomic status (Kind et al., 2018). A follow-up questionnaire will be administered to parent/legal guardian/caregiver at post-treatment, 5-months, and 12-months to obtain information about utilization of services during the intervention and follow-up periods.

**School Staff Demographic Form** – School partners and teachers will complete a demographics questionnaire to collect information regarding staff members' educational experience and background, to help characterize the school staff sample, as well as to collect information regarding about TAU organizational skills interventions offered in TAU by their schools.

**Trainer Demographic Form** – Trainers will complete a demographic form to collect information regarding trainers' educational experience and background.

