### 2.2 Secondary Objectives (or Aims)

The secondary objectives of this study are:

- Explore whether reductions in student OTMP skills deficits and improvements in student academic self-efficacy mediate the effect of OST-S on students' academic outcomes.
- Investigate whether school partner implementation fidelity and participant engagement (student, parent, teacher) are associated with the effect of OST-S on student OTMP skills deficits.
- Investigate whether student grade level, special education status, and symptoms of ADHD, externalizing, internalizing problems, and symptoms of autism spectrum disorder moderate the effect of OST-S on student OTMP skills.
- Determine the costs associated with providing the OST-S intervention per group per school relative to student proximal (OTMP skills, self-efficacy) and distal (academic productivity and grades) outcomes.
- Investigate child in-session engagement in the OST-S intervention and the clinical factors associated with child engagement

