#### **3.4.7 Inclusion Criteria for Parents/Legal Guardians**

One parent/guardian for each student enrolled in the study will complete forms for students at baseline, post-treatment and 5- and 12-month follow-up and will participate in the parent consultation portion of the intervention. Parents/guardians will consent prior to student enrollment in the study.

---

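### Autism symptoms are a named moderator, but the ASRS is rated once and only after treatment, so its interaction with OST-S can be biased

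*Protocol*

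**What the plan says.** Protocol section 2.2 sets a secondary objective of testing whether several student characteristics, including "symptoms of autism spectrum disorder moderate the effect of OST-S on student OTMP skills". 

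Section 5.4 (Measures of School and Participant Characteristics) and Table 1 fix when the autism measure is taken. Parents "will be asked to complete this measure at post-treatment to reduce the burden on parents at the time of baseline data collection". If that fails, "it will be collected at either the 5-month follow-up or 12-month follow-up time-point". There is no other rating: "This measure will only be administered to the parent once about the student during the duration of study participation". The areas covered are given as "socialization, communication, unusual behaviors, behavioral rigidity, sensory sensitivity, and self-regulation". Under section 3.4.7 the parent who completes the forms also "will participate in the parent consultation portion of the intervention".

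The BASC-3 is scheduled at baseline and is used to "derive an index of ADHD, aggression, and internalizing problems for examination of potential moderation effects". It too may be late: "If this measure is unable to be collected at baseline, an attempt will be made to collect it at a subsequent timepoint".

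Section 6.1.1, Aim 5, estimates effect modification within the mixed models. It does not restrict moderators to pre-treatment values, and its list omits autism symptoms. Aim 4 in the same section treats fidelity and engagement as post-randomization variables and keeps their analysis largely descriptive. The SAP describes no moderator analysis.

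**The concern.** A moderator should describe the student before treatment can act. If treatment can change the score, grouping students by it partly groups them by how well they responded, and it does so in one arm only.

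The documents leave a route for this. In the OST-S arm the ASRS rater has taken part in parent meetings. The scale includes self-regulation, and a Student Self-Regulation factor (HPQ-T, section 5.3) is among the trial's outcomes. COSS-P is completed by the same adult at the same assessment. A student who improves may be rated lower on the ASRS because of the improvement. Responders then collect at the low-symptom end in OST-S, with no matching movement in TAU, and OST-S appears weaker in students with more autism symptoms. With only one rating, no pre-treatment score exists with which to detect or correct this.

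At stake is a secondary finding about which students benefit. For the BASC-3 moderators, only students rated late are affected.

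**Working it through.** **1. The plan's own moderation figure.** Section 6.1.5 states power above 85% for an interaction of 0.67 SD with a modifier of 25% prevalence. Take n = 120 per arm, two-sided 5% (assumed; none is stated for moderation) and a design effect DE:

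SE = SD × √DE × √(2/(0.25n) + 2/(0.75n)), where the last factor is √(2/30 + 2/90) = 0.298.

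- SD 0.6, DE 1.11: SE = 0.6 × 1.054 × 0.298 = 0.188; power = Φ(0.67/0.188 − 1.96) = 94.5%.
- SD 0.8, DE 1.11: SE = 0.251; power = 76%.
- SD 1.0, DE 1.11: SE = 0.314; power = 57%.

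The three SDs are those printed in section 6.1.4. The sample size and SD behind the stated figure are not given, so it can be neither confirmed nor called wrong. The present point does not depend on it.

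**2. Inputs for the bias check.** From the protocol: 120 students per arm, mean effect 0.5 SD, within-student correlation 0.6. Assumed: response SD s = 0.3 or 0.5, and a carry-over fraction c (the share of a student's response that lowers the ASRS rating). No true moderation; no clustering.

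**3. Model.** Improvement y = t·R + e, with t = 1 in OST-S and 0 in TAU, R ~ N(0.5, s) and Var(e) = 2(1 − 0.6) = 0.8. Pre-treatment trait A ~ N(0, 1), independent of R. Rated moderator M = A − c·t·R.

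- In TAU, M = A, and the slope of y on M is 0.
- In OST-S, Cov(y, M) = −c·s² and Var(M) = 1 + c²s².
- The false interaction is therefore b = −c·s²/(1 + c²s²).
- SE = √[(s² + 0.8 − b²·Var(M))/(120·Var(M)) + 0.8/120].
- Rejection rate ≈ Φ(|b|/SE − 1.96) + Φ(−|b|/SE − 1.96).

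Example, s = 0.5 and c = 1: Var(M) = 1.25; b = −0.25/1.25 = −0.20; SE = √(1.00/150 + 0.8/120) = 0.1155; ratio 1.73; rejection 41%.

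| s | c | b (SD per SD of trait) | Rejection, formula | Rejection, simulation (two runs of 3,000 trials) |
|---|---|---|---|---|
| 0.5 | 0 | 0 | 5.0% | 4.4%, 4.4% |
| 0.5 | 0.2 | −0.05 | 6.9% | 6.6%, 6.9% |
| 0.5 | 0.5 | −0.12 | 16.2% | 17.1%, 16.1% |
| 0.5 | 1.0 | −0.20 | 41.0% | 39.7%, 40.2% |
| 0.3 | 0.2 | −0.02 | 5.3% | 5.5%, 5.2% |
| 0.3 | 0.5 | −0.04 | 6.6% | 6.6%, 6.7% |
| 0.3 | 1.0 | −0.08 | 11.0% | 10.1%, 10.7% |

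**4. When the bias vanishes.** If every student responds alike (s = 0), treatment shifts the ASRS uniformly, and b = 0 for any c. If the ASRS is a stable trait (c = 0), b = 0 for any s. Simulated uniform shifts of 0.2 to 0.5 SD gave rejection rates of 4.6–5.6%.

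**5. Sensitivity.** Section 6.1.4 prints 0.8 as the SD of change at correlation 0.6, whereas √0.8 = 0.894 was used above. Putting Var(e) = 0.64 into the same formulas gives about 5–7%, 7–19% and 12–48% at c = 0.2, 0.5 and 1. In a second construction the rating falls by 0.3 to 0.5 SD per SD of the child's own improvement. With response SD 0.5, it gave 8–12% for a top-quartile moderator; with response SD 0.8, 17–36%. Clustering was left out; section 6.1.5 itself expects a lower design effect for this kind of interaction than for the main effect.

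**The case against.** Five objections deserve weight.

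- **Thin mechanism.** Self-regulation is one of six areas named for a 15-item autism scale, and the HPQ-T factor is a teacher rating of homework behaviour. Nothing in the documents says an 8-week organizational program changes communication or sensory sensitivity. If about one area in six carried over (c = 0.17, a rough assumption), the formula gives 6.3% at s = 0.5 and 5.2% at s = 0.3, close to nominal. For COSS-T the outcome rater is the teacher, so shared-rater bias does not apply directly. This stands, and it is why the size must be called unknown.
- **The 40% figure.** A reader might take it as the expected error rate. It needs full carry-over and s = 0.5, and the documents support neither. If the rating follows all improvement in both arms and not only the treatment-caused part, the rate at full carry-over falls to about 17% (s = 0.5) or 7% (s = 0.3).
- **Late measurement as such.** A reader might infer that any interaction with a variable measured after treatment is invalid. That goes too far: a stable trait measured late can still be a valid moderator. The protocol does not argue stability, however; its stated reason for the timing is parent burden.
- **What Aim 5 says.** A reader might infer that it treats the ASRS as a baseline modifier. It neither uses that word for its moderators nor lists autism symptoms. The planned use rests on section 2.2 alone, and this mismatch is itself a documented gap.
- **BASC-3.** Baseline is the rule and late collection a contingency of unknown frequency. Dropping late-rated students selects on completion, so their ratings are better shown in a sensitivity analysis than discarded.

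**Conclusion.** The point holds as a limited one. Autism symptoms are a named moderator, the only ASRS rating comes after treatment, the rating parent in the OST-S arm has taken part in the intervention, and neither document restricts moderators to pre-treatment values. Following the plan can therefore yield a biased interaction, in the direction of a smaller apparent benefit for students with more autism symptoms.

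The bias requires that responses differ between students and that the rating tracks them. Neither quantity is documented. On the assumed range, the false-positive rate runs from near nominal to 10–40% in the extreme case of full carry-over.

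A reader might go on to infer that the trial's efficacy result is compromised, or that schools will be steered away from offering OST-S to these students. The documents support neither: the aim is secondary and exploratory, the primary comparison does not use the ASRS, and no such use of the result is described. The change is worth making as a cheap improvement.

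**What to change.** 1. Reconcile section 2.2 with Aim 5 in section 6.1.1: state whether autism symptoms are a moderator, and give one list.
2. Move the 15-item ASRS Short Form to the baseline parent packet in Table 1 and section 5.4, and use as moderators only ratings made before the intervention period starts, in both arms. A cut-off tied to a paired school would not suit every school, because section 8.1.1 allows additional schools and altered allocation ratios.
3. For students whose ASRS was collected after treatment, report scores by arm, label the ASRS a post-randomization variable as Aim 4 does for fidelity and engagement, and draw no moderation conclusion from it. The SAP, dated June 2022, already reports 12-month data, so for students already followed up this is the only usable part of the ASRS remedy.
4. Base BASC-3 moderation on pre-treatment ratings, adding late ratings only in a sensitivity analysis.

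The cost is fifteen more parent items at baseline, the burden the protocol wanted to defer, against one fewer form at post-treatment. Students with late BASC-3 forms leave the main moderation model. For data already collected, the cost is an analysis rule and a table of ASRS scores by arm.
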